## 2. Hypersensitivity Reactions (HSR)

Medical concept of hypersensitivity reactions/DRESS. Only narrow terms selected from Category A of SMQ 'Drug reaction with eosinophilia and systemic symptoms syndrome'. Algorithmic approach for this SMQ not used due to complexity in applying and poor specificity of remaining categories. Category A selected as PTs because more specific for concept (only narrow terms) and a pre-requisite for any combination in algorithmic search. Overlap of some preferred terms with SMQ 'Severe Cutaneous Adverse Reactions'. Plus, additional preferred terms selected from HGLT 'Allergic conditions' under SOC 'Immune system disorders.

SMQ: Drug reaction with eosinophilia and systemic symptoms syndrome SMQ Code: 20000225 Category: A Scope: Narrow	
Preferred Term	PT Code
Drug reaction with eosinophilia and systemic symptoms	10073508
Pseudolymphoma	10037127
Additional preferred terms selected from HLGT 'Allergic conditions' under SOC 'Immune system disorders'	
Preferred Term	PT Code
Drug hypersensitivity	10013700
Hypersensitivity	10020751
Type IV Hypersensitivity reaction	10053613
Eosinophillia	10014950
Eye swelling	10015967
Eyelid oedema	10015993
Lip swelling	10024570
Angioedema	10002424

Circumoral oedema	10052250
Face oedema	10016029
Idiopathic angioedema	10073257
Lip oedema	10024558
Mouth swelling	10075203
Oedema mouth	10030110
Periorbital oedema	10034545
Swelling face	10042682
Periorbital swelling	10056647
Swelling of eyelid	10042690

# 3. Rash including severe cutaneous adverse reactions

Medical concept of rash including severe cutaneous adverse reactions. Only narrow terms from SMQ 'Severe cutaneous adverse reactions' selected. Plus several additional preferred terms selected from HLTs 'Rashes, eruptions and exanthems NEC', 'Pruritus NEC', 'Pustular conditions', 'Dermatitis ascribed to specific agent' all under SOC 'Skin and subcutaneous tissue disorders'.

SMQ: Severe Cutaneous Adverse Reactions SMQ Code: 20000020 Category: A Scope: Narrow	
SMQ	PT Code
Acute generalised exanthematous pustulosis	10048799
Cutaneous vasculitis	10011686
Dermatitis bullous	10012441
Dermatitis exfoliative	10012455
Dermatitis exfoliative generalised	10012456
Drug reaction with eosinophilia and systemic symptoms	10073508
Epidermal necrosis	10059284
Erythema multiforme	10015218
Exfoliative rash	10064579

Oculomucocutaneous syndrome	10030081
Skin necrosis	10040893
Stevens-Johnson syndrome	10042033
Target skin lesion	10081998
Toxic epidermal necrolysis	10044223
Toxic skin eruption	10057970
Additional preferred terms selected from HLTs 'Rashes, eruptions and exanthems NEC', 'Pruritus NEC', 'Pustular conditions', 'Dermatitis ascribed to specific agent' all under SOC 'Skin and subcutaneous tissue disorders'.	
Preferred Term	PT Code
Eyelid rash	10074620
Genital rash	10018175
Mucocutaneous rash	10056671
Nodular rash	10075807
Perineal rash	10075364
Rash	10037844
Rash erythematous	10037855
Rash generalised	10037858
Rash macular	10037867
Rash maculo-papular	10037868
Rash maculovesicular	10050004
Rash morbilliform	10037870
Rash papular	10037876
Rash rubelliform	10057984
Rash scarlatiniform	10037890
Rash vesicular	10037898
Rash pruritic	10037884
Rash follicular	10037857
Rash pustular	10037888

## 4. Prolongation of the Corrected QT Interval of the ECG in Supratherapeutic Doses

Notes: Medical concept of QT prolongation and complications. Only narrow terms from SMQ 'Torsade de pointes/QT prolongation' selected plus one additional PT under HLT 'ECG investigations'.

SMQ: Torsade de pointes/QT prolongation SMQ Code: 20000001 Category: A Scope: Narrow	
Preferred Term	PT Code
Electrocardiogram QT interval abnormal	10063748
Electrocardiogram QT prolonged	10014387
Long QT syndrome	10024803
Long QT syndrome congenital	10057926
Torsade de pointes	10044066
Ventricular tachycardia	10047302
Additional preferred terms selected from HGLT ' ECG investigations' under SOC 'Investigations'.	
Preferred Term	PT Code
Electrocardiogram repolarisation abnormality	10052464

### 5. Suicidal Ideation/Behaviour

Medical concept of suicidal ideation and behaviour. Sub-SMQ 'Suicide/self-injury' (SMQ) from parent SMQ of 'Depression and Suicide/Self Injury'. Only narrow terms from the sub-SMQ selected.

SMQ: 'Depression and Suicide/Self Injury' SMQ Code: 20000035 Sub-SMQ: 'Suicide/self-injury' Category: A Scope: Narrow	
Preferred Term	PT Code
Assisted suicide	10079105
Columbia suicide severity rating scale abnormal	10075616

10010144
10012397
10022523
10022524
10036000
10051154
10065604
10042458
10042464
10077417
10082458
10081704

## 6. Depression

Medical concept of Depression. Sub-SMQ 'Depression (excl suicide and self injury)' (SMQ) from parent SMQ of 'Depression and Suicide/Self Injury'. Only narrow terms from the sub-SMQ selected.

SMQ: "Depression and Suicide/Self Injury" SMQ Code: 20000035 Sub-SMQ: 'Depression (excl suicide and self injury)' Category: A Scope: Narrow	
Preferred Term	PT Code
Activation syndrome	10066817
Adjustment disorder with depressed mood	10001297
Adjustment disorder with mixed anxiety and depressed mood	10001299
Agitated depression	10001496
Anhedonia	10002511
Antidepressant therapy	10054976
Childhood depression	10068631
Decreased interest	10011971

Depressed mood	10012374
Depression	10012378
Depression postoperative	10012390
Depressive symptom	10054089
Dysphoria	10013954
Electroconvulsive therapy	10014404
Feeling guilty	10049708
Feeling of despair	10016344
Feelings of worthlessness	10016374
Helplessness	10077169
Major depression	10057840
Menopausal depression	10067371
Mixed anxiety and depressive disorder	10080836
Perinatal depression	10078366
Persistent depressive disorder	10077804
Post stroke depression	10070606
Postictal depression	10071324

## 7. Bipolar Disorder

Medical concept of bipolar disorder. All preferred terms from HLGT 'Manic and Bipolar mood disorders and disturbances' under SOC 'Psychiatric disorders'.

Preferred Term	PT Code
Bipolar I disorder	10004939
Bipolar II disorder	10004940
Bipolar disorder	10057667
Cyclothymic disorder	10011724
Hypomania	10021030
Mania	10026749

# 8. Psychosis

Medical concept of psychosis. Only narrow terms from SMQ 'Psychosis and psychotic disorders' selected.

SMQ: 'Psychosis and psychotic disorders' SMQ Code: 20000117 Category: A Scope: Narrow	
Preferred Term	PT Code
Acute psychosis	10001022
Alcoholic psychosis	10001632
Alice in wonderland syndrome	10001666
Brief psychotic disorder with marked stressors	10048549
Brief psychotic disorder without marked stressors	10056395
Brief psychotic disorder, with postpartum onset	10006362
Charles Bonnet syndrome	10063354
Childhood psychosis	10061040
Clang associations	10009232
Cotard's syndrome	10059591
Delusion	10012239
Delusion of grandeur	10012241
Delusion of reference	10012244
Delusion of replacement	10012245
Delusional disorder, erotomanic type	10012249
Delusional disorder, grandiose type	10012250
Delusional disorder, jealous type	10012251
Delusional disorder, mixed type	10012252
Delusional disorder, persecutory type	10053195
Delusional disorder, somatic type	10012254
Delusional disorder, unspecified type	10012255
Delusional perception	10012258

Dementia of the Alzheimer's type, with delusions	10012295
Depressive delusion	10063033
Derailment	10012411
Epileptic psychosis	10059232
Erotomanic delusion	10015134
Flight of ideas	10016777
Hallucination	10019063
Hallucination, auditory	10019070
Hallucination, gustatory	10019071
Hallucination, olfactory	10019072
Hallucination, synaesthetic	10062824
Hallucination, tactile	10019074
Hallucination, visual	10019075
Hallucinations, mixed	10019079
Hypnagogic hallucination	10020927
Hypnopompic hallucination	10020928
Hysterical psychosis	10062645
Ideas of reference	10021212
Illusion	10021403
Jealous delusion	10023164
Loose associations	10024825
Mixed delusion	10076429
Neologism	10028916
Neuroleptic-induced deficit syndrome	10075295
Paranoia	10033864
Paranoid personality disorder	10033869
Parkinson's disease psychosis	10074835
Paroxysmal perceptual alteration	10063117
Persecutory delusion	10034702

Post-injection delirium sedation syndrome         10070669           Post-injection delirium sedation syndrome         10072851           Posturing         10036437           Psychosis postoperative         10065617           Psychotic behaviour         10037249           Psychotic disorder         10061920           Psychotic disorder due to a general medical condition         10061921           Reactive psychosis         10053632           Rebound psychosis         10074833           Schizoaffective disorder         10039621           Schizoaffective disorder bipolar type         10068890           Schizophrenia         10039626           Schizophreniform disorder         10039647           Schizotypal personality disorder         10039651           Senile psychotic disorder         10040535
Posturing 10036437 Psychosis postoperative 10065617 Psychotic behaviour 10037249 Psychotic disorder 10061920 Psychotic disorder due to a general medical condition 10061921 Reactive psychosis 10053632 Rebound psychosis 10074833 Schizoaffective disorder 10039621 Schizoaffective disorder bipolar type 10068889 Schizoaffective disorder depressive type 10068890 Schizophrenia 10039626 Schizophreniform disorder 10039651 Senile psychosis 10039987 Shared psychotic disorder 10040535
Psychosis postoperative 10065617 Psychotic behaviour 10037249 Psychotic disorder 10061920 Psychotic disorder due to a general medical condition 10061921 Reactive psychosis 10053632 Rebound psychosis 10074833 Schizoaffective disorder 10039621 Schizoaffective disorder 10068889 Schizoaffective disorder depressive type 10068890 Schizophrenia 10039626 Schizophreniform disorder 10039647 Schizotypal personality disorder 10039987 Shared psychotic disorder 10040535
Psychotic behaviour 10037249 Psychotic disorder 10061920 Psychotic disorder due to a general medical condition 10061921 Reactive psychosis 10053632 Rebound psychosis 10074833 Schizoaffective disorder 10039621 Schizoaffective disorder bipolar type 10068899 Schizoaffective disorder depressive type 10068890 Schizophrenia 10039626 Schizophrenia 10039647 Schizotypal personality disorder 10039987 Shared psychotic disorder 10040535
Psychotic disorder 10061920 Psychotic disorder due to a general medical condition 10061921 Reactive psychosis 10053632 Rebound psychosis 10074833 Schizoaffective disorder 10039621 Schizoaffective disorder bipolar type 10068889 Schizoaffective disorder depressive type 10068890 Schizophrenia 10039626 Schizophreniform disorder 10039647 Schizotypal personality disorder 10039987 Shared psychotic disorder 10040535
Psychotic disorder due to a general medical condition  Reactive psychosis  Rebound psychosis  10074833  Schizoaffective disorder  10039621  Schizoaffective disorder bipolar type  10068889  Schizoaffective disorder depressive type  10068890  Schizophrenia  10039626  Schizophreniform disorder  10039647  Schizotypal personality disorder  10039987  Shared psychotic disorder  10040535
Reactive psychosis 10053632 Rebound psychosis 10074833 Schizoaffective disorder 10039621 Schizoaffective disorder bipolar type 10068889 Schizoaffective disorder depressive type 10068890 Schizophrenia 10039626 Schizophreniform disorder 10039647 Schizotypal personality disorder 10039651 Senile psychosis 10039987 Shared psychotic disorder 10040535
Rebound psychosis 10074833 Schizoaffective disorder 10039621 Schizoaffective disorder bipolar type 10068889 Schizoaffective disorder depressive type 10068890 Schizophrenia 10039626 Schizophreniform disorder 10039647 Schizotypal personality disorder 10039651 Senile psychosis 10039987 Shared psychotic disorder 10040535
Schizoaffective disorder10039621Schizoaffective disorder bipolar type10068889Schizoaffective disorder depressive type10068890Schizophrenia10039626Schizophreniform disorder10039647Schizotypal personality disorder10039651Senile psychosis10039987Shared psychotic disorder10040535
Schizoaffective disorder bipolar type  Schizoaffective disorder depressive type  10068890  Schizophrenia  10039626  Schizophreniform disorder  10039647  Schizotypal personality disorder  10039651  Senile psychosis  10039987  Shared psychotic disorder  10040535
Schizoaffective disorder depressive type  Schizophrenia  10039626  Schizophreniform disorder  10039647  Schizotypal personality disorder  Senile psychosis  10039987  Shared psychotic disorder  10040535
Schizophrenia 10039626 Schizophreniform disorder 10039647 Schizotypal personality disorder 10039651 Senile psychosis 10039987 Shared psychotic disorder 10040535
Schizophreniform disorder 10039647 Schizotypal personality disorder 10039651 Senile psychosis 10039987 Shared psychotic disorder 10040535
Schizotypal personality disorder 10039651 Senile psychosis 10039987 Shared psychotic disorder 10040535
Senile psychosis 10039987 Shared psychotic disorder 10040535
Shared psychotic disorder 10040535
0 5 11 5
Somatic delusion 10041317
Somatic hallucination 10062684
Substance-induced psychotic disorder 10072388
Tangentiality 10043114
Thought blocking 10043495
Thought broadcasting 10052214
Thought insertion 10043496
Thought withdrawal 10043497
Transient psychosis 10056326
Waxy flexibility 10047853

# 9. Mood Disorders

Medical concept of mood disorders. All preferred terms from HLGT 'Mood disorders and disturbances NEC', under SOC 'Psychiatric disorders'.

Preferred Term	PT Code
Affect lability	10054196
Affective ambivalence	10077173
Affective disorder	10001443
Alexithymia	10077719
Anger	10002368
Apathy	10002942
Blunted affect	10005885
Boredom	10048909
Constricted affect	10010778
Crying	10011469
Diencephalic syndrome of infancy	10012774
Dysphoria	10013954
Emotional disorder	10014551
Emotional distress	10049119
Emotional poverty	10014557
Euphoric mood	10015535
Flat affect	10016759
Frustration tolerance decreased	10077753
Inappropriate affect	10021588
Irritability	10022998
Laziness	10051602
Lethargy	10024264
Listless	10024642
Moaning	10027783
Mood altered	10027940

Mood disorder due to a general medical condition	10027944
Mood swings	10027951
Morose	10027977
Neuroleptic-induced deficit syndrome	10075295
Premenstrual dysphoric disorder	10051537
Premenstrual syndrome	10036618
Screaming	10039740
Seasonal affective disorder	10039775
Steroid withdrawal syndrome	10042028
Substance-induced mood disorder	10072387

# 10. Anxiety

Notes: Medical concept of anxiety disorders. All preferred terms from HLGT "Anxiety disorders and symptoms", under SOC "Psychiatric disorders".

Preferred Terms	PT Code
Acrophobia	10000605
Activation syndrome	10066817
Acute stress disorder	10001084
Aerophobia	10080300
Agitation	10001497
Agitation postoperative	10049989
Agoraphobia	10001502
Akathisia	10001540
Algophobia	10078056
Animal phobia	10002518
Anniversary reaction	10074066
Anticipatory anxiety	10002758
Anxiety	10002855
Anxiety disorder	10057666

Anxiety disorder due to a general medical condition	10002859
Arachnophobia	10051408
Astraphobia	10078372
Autophobia	10071070
Body dysmorphic disorder	10052793
Burnout syndrome	10065369
Catastrophic reaction	10082329
Cibophobia	10082413
Claustrophobia	10009244
Compulsions	10010219
Compulsive cheek biting	10076510
Compulsive handwashing	10071263
Compulsive hoarding	10068007
Compulsive lip biting	10066241
Compulsive shopping	10067948
Dermatillomania	10065701
Dysmorphophobia	10049096
Emetophobia	10070637
Fear	10016275
Fear of animals	10016276
Fear of closed spaces	10016277
Fear of crowded places	10050365
Fear of death	10066392
Fear of disease	10016278
Fear of eating	10050366
Fear of falling	10048744
Fear of injection	10073753
Fear of open spaces	10016279
Fear of pregnancy	10067035

Fear of weight gain	10016280
Fear-related avoidance of activities	10080136
Generalised anxiety disorder	10018075
Glossophobia	10080077
Haemophobia	10073458
Haphephobia	10067580
Herpetophobia	10081809
Hydrophobia	10053317
Hyperarousal	10080831
Immunisation anxiety related reaction	10075205
Kinesiophobia	10078430
Limited symptom panic attack	10024511
Mysophobia	10078769
Nail picking	10066779
Nervousness	10029216
Neurosis	10029333
Noctiphobia	10057946
Nocturnal fear	10057948
Nosophobia	10063546
Obsessive need for symmetry	10077179
Obsessive rumination	10056264
Obsessive thoughts	10029897
Obsessive-compulsive disorder	10029898
Obsessive-compulsive symptom	10077894
Ochlophobia	10050095
Osmophobia	10060765
Paediatric autoimmune neuropsychiatric disorders associated with streptococcal infection	10072147
Panic attack	10033664

Panic disorder	10033666
Panic reaction	10033670
Paruresis	10069024
Performance fear	10034432
Phagophobia	10050096
Pharmacophobia	10069423
Phobia	10034912
Phobia of driving	10056676
Phobia of exams	10034913
Phobic avoidance	10034918
Phonophobia	10054956
Photaugiaphobia	10064420
Postpartum anxiety	10082233
Postpartum neurosis	10036419
Postpartum stress disorder	10056394
Post-traumatic stress disorder	10036316
Procedural anxiety	10075204
Pseudoangina	10056610
Selective mutism	10039917
Separation anxiety disorder	10040045
Sitophobia	10080170
Social anxiety disorder	10041242
Social fear	10041247
Stress	10042209
Tension	10043268
Terminal agitation	10077416
Thanatophobia	10064723
Thermophobia	10075147
Trichotemnomania	10072752

Trichotillomania	10044629
------------------	----------

## 11. Sleep Disorders

Medical concept of sleep disorders. All preferred terms from (1) HLGT 'Sleep Disorders and Disturbances', 'Psychiatric disorders' SOC plus (2) HLGT 'Sleep disturbances (including subtypes)', 'Nervous system' SOC. Numerous duplicated preferred terms e.g. middle insomnia.

HLGT Sleep Disorders and Disturbances, HLGT Code 10040991	
Preferred Term	PT Code
Abnormal dreams	10000125
Abnormal sleep-related event	10061613
Advanced sleep phase	10001423
Behavioural induced insufficient sleep syndrome	10081938
Behavioural insomnia of childhood	10072072
Breathing-related sleep disorder	10006344
Cataplexy	10007737
Circadian rhythm sleep disorder	10009191
Confusional arousal	10067494
Delayed sleep phase	10012209
Dyssomnia	10061827
Exploding head syndrome	10080684
Hypersomnia	10020765
Hypersomnia related to another mental condition	10020767
Hypersomnia-bulimia syndrome	10053712
Hypnagogic hallucination	10020927
Hypnopompic hallucination	10020928
Hyposomnia	10067530
Initial insomnia	10022035
Insomnia	10022437
Insomnia related to another mental condition	10022443

Irregular sleep phase	10022995
Irregular sleep wake rhythm disorder	10080301
Loss of dreaming	10065085
Middle insomnia	10027590
Narcolepsy	10028713
Nightmare	10029412
Non-24-hour sleep-wake disorder	10078086
Parasomnia	10061910
Periodic limb movement disorder	10064600
Pickwickian syndrome	10035004
Poor quality sleep	10062519
Rapid eye movement sleep behaviour disorder	10077299
Rapid eye movements sleep abnormal	10037841
Shift work disorder	10078088
Sleep apnoea syndrome	10040979
Sleep attacks	10040981
Sleep disorder	10040984
Sleep disorder due to a general medical condition	10063910
Sleep disorder due to general medical condition, hypersomnia type	10040985
Sleep disorder due to general medical condition, insomnia type	10040986
Sleep disorder due to general medical condition, mixed type	10040987
Sleep disorder due to general medical condition, parasomnia type	10040988
Sleep inertia	10067493
Sleep paralysis	10041002
Sleep sex	10067492
Sleep talking	10041009
Sleep terror	10041010
Sleep-related eating disorder	10067315
Somnambulism	10041347
	•

Somnolence	10041349
Somnolence neonatal	10041350
Sopor	10058709
Stupor	10042264
Terminal insomnia	10068932
Upper airway resistance syndrome	10063968
HLGT Sleep disturbances (incl subtypes), HLGT code 10040998	
Abnormal dreams	10000125
Abnormal sleep-related event	10061613
Advanced sleep phase	10001423
Behavioural induced insufficient sleep syndrome	10081938
Behavioural insomnia of childhood	10072072
Breathing-related sleep disorder	10006344
Cataplexy	10007737
Central-alveolar hypoventilation	10007982
Circadian rhythm sleep disorder	10009191
Confusional arousal	10067494
Delayed sleep phase	10012209
Dyssomnia	10061827
Fatal familial insomnia	10072077
Hypersomnia	10020765
Hyposomnia	10067530
Initial insomnia	10022035
Insomnia	10022437
Irregular sleep phase	10022995
Irregular sleep wake rhythm disorder	10080301
Loss of dreaming	10065085
Microsleep	10076954
Middle insomnia	10027590

	•
Narcolepsy	10028713
Non-24-hour sleep-wake disorder	10078086
Periodic limb movement disorder	10064600
Pickwickian syndrome	10035004
Poor quality sleep	10062519
Rapid eye movement sleep behaviour disorder	10077299
Rapid eye movements sleep abnormal	10037841
Shift work disorder	10078088
Sleep apnoea syndrome	10040979
Sleep deficit	10080881
Sleep inertia	10067493
Sleep paralysis	10041002
Sleep sex	10067492
Sleep talking	10041009
Sleep terror	10041010
Sleep-related eating disorder	10067315
Somnambulism	10041347
Sudden onset of sleep	10050014
Terminal insomnia	10068932
Upper airway resistance syndrome	10063968

## 12. Injection Site Reactions (ISR) from Study Drug Injections

Study drug ISR data available in the database, i.e. data collected from non-serious ISR AE eCRF form and collected serious adverse events with 'STUDY DRUG INJECTION SITE' included in the AE term.

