Injection Site Reactions	
Clinical, experience to date has demonstrated ISRs occur in the majority of exposed participants treated with RPV LA but are generally mild (Grade 1) or moderate (Grade 2) and include events of pain, tenderness, erythema, or nodule formation of several days duration (median duration for individual events <1 week). ISRs may occur more than once in an individual participant receiving multiple injections. Although some Grade 3 ISRs were reported, overall ISRs have been well tolerated and have not to date been associated with an excess of participants' withdrawal due to ISRs.
 
None of the ISRs was serious and no clinical significant complications were reported
	
 • Administration advice to minimize risk of poor administration technique giving rise to injection site reactions. Advice on care, monitoring, natural course, and treatment of ISRs given in study documentation • Advice to participants on care of injection site on day/days immediately post administration, use of analgesia, compresses where appropriate. • Participants will be closely monitored for ISRs particularly for signs of pain, tenderness, infections, erythema, swelling, induration, or nodules (granulomas or cysts) throughout the study. • Complications of ISRs such as infections (abscess, cellulitis) and collections of fluid requiring drainage will be monitored • Significant ISRs may be photographed and referred to a dermatologist for specialist advice.

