- Injection Site Reactions (ISRs) will be assessed clinically during the Maintenance and Extension Phases for the following:
Pain, tenderness, pruritis, warmth, bruising, discoloration, infections, rash, erythema, swelling, induration, and nodules (granulomas or cysts).
- A clinical assessment (using Division of Acquired Immunodeficiency Syndrome [DAIDS] grading scale) should be performed both before and after an injection to identify resolving and new ISRs. All injection site reactions are considered adverse events. The clinical assessment and interpretation of any ISR, will be documented in the ISR AE eCRF.

Any appropriately qualified site personnel (e.g., Investigator, sub-Investigator, or study coordinator/nurse) can perform assessments.

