12.4.4. Recording and Follow-Up of AE and SAE

AE and SAE Recording

- When an AE/SAE occurs, it is the responsibility of the investigator to review all documentation (eg, hospital progress notes, laboratory, and diagnostics reports) related to the event.
- The investigator will then record all relevant AE/SAE information in the CRF.
- It is **not** acceptable for the investigator to send photocopies of the participant's medical records to GSK in lieu of completion of the GSK /AE/SAE CRF page.
- There may be instances when copies of medical records for certain cases are requested by GSK. In this case, all participant identifiers, with the exception of the participant number, will be redacted on the copies of the medical records before submission to GSK.
- The investigator will attempt to establish a diagnosis of the event based on signs, symptoms, and/or other clinical information. Whenever possible, the diagnosis (not the individual signs/symptoms) will be documented as the AE/SAE.

Assessment of Intensity

The investigator will make an assessment of intensity for each AE and SAE reported during the study and assign it to 1 of the following categories:

- **Mild:** An event that is easily tolerated by the participant, causing minimal discomfort and not interfering with everyday activities.
- **Moderate:** An event that causes sufficient discomfort and interferes with normal everyday activities.
- **Severe:** An event that prevents normal everyday activities. An AE that is assessed as severe should not be confused with an SAE. Severe is a category utilized for rating the intensity of an event; and both AE and SAE can be assessed as severe.

An event is defined as 'serious' when it meets at least 1 of the predefined outcomes as described in the definition of an SAE, NOT when it is rated as severe.

Assessment of Causality

- The investigator is obligated to assess the relationship between study intervention and each occurrence of each AE/SAE.
- A "reasonable possibility" of a relationship conveys that there are facts, evidence, and/or arguments to suggest a causal relationship, rather than a relationship cannot be ruled out.
- The investigator will use clinical judgment to determine the relationship.
- Alternative causes, such as underlying disease(s), concomitant therapy, and other risk factors, as well as the temporal relationship of the event to study intervention administration will be considered and investigated.

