12.10.6.2. Capturing COVID-19 Specific AEs and SAEs

It is important for the study team to describe COVID-19 related adverse events/serious adverse and their impact on study data and outcomes. Standardization of case definitions will facilitate future data analysis.

Please use the following guidance:

1. AEs should continue to be evaluated as to whether they meet SAE criteria as defined in the protocol, and if so, submitted according to established SAE reporting requirements. SAEs and AEs should be submitted following usual study procedures and timelines.

2. When an in-person clinic visit is not possible, please conduct a remote telehealth visit to assess for, and document any AEs/SAEs.
3. Investigators should use the WHO definition to classify COVID-19 cases. The definition below, released March 20, 2020, represents a time point for standardized collection. We recognize definitions are likely to continue to evolve. When reporting both serious and non-serious adverse events (related to COVID-19 infection, investigators should use the following Verbatim terms:
 - a) Suspected COVID-19 infection; or
 - b) Probable COVID-19 infection; or
 - c) Confirmed COVID-19 infection
4. Sites should contact the study Medical Monitor for questions related to definitions and reporting, and decisions around impact to study drug continuation.
5. A new COVID-19 infection Case Report Form will be added to the eCRF to collect additional details about the reported COVID-19 AE or SAE data. It is important to collect the correct information from each participant reporting a COVID-19 AE or SAE. Therefore, please use the CRF templates to help you collect this information, once available.

WHO Case Definition - March 20, 2020 Version ([https://www.who.int/publications-detail/global-surveillance-for-human-infection-with-novel-coronavirus-\(2019-ncov\)](https://www.who.int/publications-detail/global-surveillance-for-human-infection-with-novel-coronavirus-(2019-ncov))):

Suspected case:

- A. A patient with acute respiratory illness (fever and at least one sign/symptom of respiratory disease, e.g., cough, shortness of breath), AND a history of travel to or residence in a location reporting community transmission of COVID-19 disease during the 14 days prior to symptom onset;

OR

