## 12.12.8. Safety Figures

Safety	: Figures				
No.	Population	IDSL / Example Shell	Title	Programming Notes	Deliverable
Advers	se Events				
3.01.	Safety	207966/primar y_02/F3.1	Plot of Common Adverse Events and Relative Risk – Q2M vs. DTG + RPV - Excluding Study Drug ISRs		M12, M26, EOS
Study	Drug Injection	Site Reaction A	dverse Events (display for Q2M arm only)		
3.02.	Safety	207966/primar y_02/F3.2	Plot of Common Study Drug Injection Site Reaction Adverse Events	Only display first panel	M12, M26, EOS
3.03.	Safety	207966/primar y_02/F3.3	Plot of Onset, Duration, and Severity of Overall and Common Study Drug Injection Site Reaction AEs by Maximum Grade - CAB and/or RPV		M12, M26, EOS
3.04.	Safety	207966/primar y_02/F3.4	Plot of Onset, Duration, and Severity of Overall and Common Drug-related Study Drug Injection Site Reaction AEs by Maximum Grade - CAB		M12, M26, EOS
3.05.	Safety	207966/primar y_02/F3.5	Plot of Onset, Duration, and Severity of Overall and Common Drug-related Study Drug Injection Site Reaction AEs by Maximum Grade - RPV		M12, M26, EOS
3.06.	Safety	207966/primar y_02/F3.6	Plot of Incidence of Maintenance Phase Study Drug Injection Site Reaction Adverse Events by Visit (Overall and Common) - CAB and/or RPV		M12, M26, EOS
3.07.	Safety	207966/primar y_02/F3.7	Plot of Incidence of Maintenance Phase Drug-Related Study Drug Injection Site Reaction Adverse Events by Visit (Overall and Common) - CAB		M12, M26, EOS

Safety	: Figures				
No.	Population	IDSL / Example Shell	Title	Programming Notes	Deliverable
3.08.	Safety	207966/primar y_02/F3.8	Plot of Incidence of Maintenance Phase Drug-Related Study Drug Injection Site Reaction Adverse Events by Visit (Overall and Common) - RPV		M12, M26, EOS
3.09.	Safety	207966/primar y_02/F3.9	Plot of Incidence of Grade 3-5 Maintenance Phase Study Drug Injection Site Reaction Adverse Events by Visit (Overall and Common) - CAB and/or RPV		M12, M26, EOS
3.10.	Safety	207966/primar y_02/F3.10	Plot of Incidence of Grade 3-5 Maintenance Phase Drug- related Study Drug Injection Site Reaction Adverse Events by Visit (Overall and Common) - CAB		M12, M26, EOS
3.11.	Safety	207966/primar y_02/F3.11	Plot of Incidence of Grade 3-5 Maintenance Phase Drug- related Study Drug Injection Site Reaction Adverse Events by Visit (Overall and Common) - RPV		M12, M26, EOS
Labora	itory				
3.12.	Safety	207966/primar y_02/F3.12	Scatter Plot of Maximum vs. Baseline for ALT		M12, M26, EOS

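### As written, the SAP captures serious injection site reactions only through a literal text string in the AE term, so one recorded by its diagnosis could be absent from the dedicated ISR outputs

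*SAP*

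**What the plan says.** SAP Appendix 10, item 12, gives two sources for study-drug ISRs: an ISR eCRF form that it labels non-serious, and "collected serious adverse events with 'STUDY DRUG INJECTION SITE' included in the AE term". Unlike most other entries in that appendix, it has no MedDRA preferred-term, high-level-term or SMQ search behind it. The ISR analysis in SAP Section 8.1.1 and the displays in Sections 12.12.7 and 12.12.8 depend on this set.

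Protocol Section 8.4.1 describes the form differently: "The clinical assessment and interpretation of any ISR, will be documented in the ISR AE eCRF". It makes no split by seriousness.

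On wording, Protocol Section 12.4.4 says: "Whenever possible, the diagnosis (not the individual signs/symptoms) will be documented as the AE/SAE". Protocol Section 2.3.1 names the complications it has in mind: "Complications of ISRs such as infections (abscess, cellulitis) and collections of fluid requiring drainage will be monitored". Neither document prescribes a term for a serious ISR.

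**The concern.** A serious ISR is most likely to be a complication with a diagnosis of its own, and the protocol asks for that diagnosis. If the ISR form holds only non-serious events, as the SAP's label implies, the event then enters the ISR set only if the site happened to write four particular words. Non-serious ISRs face no such test, so any loss falls on serious events alone and goes in one direction.

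ISR incidence and severity are a central tolerability result for an injectable regimen, and Table 3.18 is among the headline deliverables. Protocol Section 2.3.1 reports no serious ISR to date with either injectable. A first case would therefore be notable, and the dedicated ISR outputs would give no sign that it was missing.

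**Working it through.** No stated figure is in dispute, so the check is mainly textual. The arithmetic serves only to show scale.

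**1. Which text is searched.** The SAP says AE term without further definition. The preferred terms it names in Section 8.1.1 (injection site pain, induration, nodules) do not contain the words STUDY DRUG. A search of coded terms would miss all of them, so the rule must refer to the term as reported by the site.

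**2. Plausible reported terms against the string.**

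| Reported term | Contains STUDY DRUG INJECTION SITE? |
|---|---|
| Gluteal abscess | No |
| Cellulitis | No |
| Injection site abscess | No (lacks STUDY DRUG) |
| Study drug injection site abscess | Yes |

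The first two follow the instruction to record a diagnosis. The third names the injection site and still fails.

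**3. Is the wording prescribed elsewhere?** For COVID-19 events, Protocol Section 12.10.6.2 says "investigators should use the following Verbatim terms" and lists them. There is no counterpart for ISRs. Protocol Sections 8.5.1 and 8.5.2 refer to Appendix 4 for the method of recording AEs and SAEs, and Appendix 4 does not contain the string. Section 8.5.4 refers to the Study Procedures Manual (SPM), which is not supplied.

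**4. Which displays a missed event would touch.** Take one serious abscess in the injection arm.
- Overall ISR displays: Tables 3.18, 3.19 and 3.20; Figures 3.03 and 3.06; and Figure 3.09 ("Plot of Incidence of Grade 3-5 Maintenance Phase Study Drug Injection Site Reaction Adverse Events by Visit") if the event is Grade 3 or higher.
- Drug-specific displays, if the event is drug-related and its side identifies the drug: Tables 3.21-3.23 with Figures 3.04, 3.07 and 3.10 for CAB, or Tables 3.25-3.27 with Figures 3.05, 3.08 and 3.11 for RPV. Figures 3.10 and 3.11 again need Grade 3 or higher.
- Not touched: Tables 3.24 and 3.28 and Figure 3.02. These show common ISRs, which Section 8.1.1 limits to pain, induration, nodules and other terms reaching 5%.

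The maximum is 3 + 3 = 6 of the 11 ISR tables (3.18-3.28) and 3 + 3 = 6 of the 10 ISR figures (3.02-3.11).

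**5. Where it would still appear.** Tables 3.01, 3.07 and 3.47, Listing 13, and Listing 16 (Listing 15 if fatal). None of these is filtered by the string.

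**6. Scale, by assumption.** About 100 participants are planned over both elected regimens (Protocol Section 10.2), so the injection arm has at most about 100. The documents give no rate for serious ISRs beyond none to date, and no denominator for that statement. If the 230 participants in the LATTE-2 injection arms (Protocol Table 1) are taken as a minimum denominator, the one-sided 95% upper bound for 0/230 is 1 − 0.05^(1/230) = 1.3%. For an assumed rate p and n = 100, the expected count is 100p and the chance of at least one case is 1 − (1 − p)^100:

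| p | Expected participants | Chance of at least one |
|---|---|---|
| 0.1% | 0.1 | 9.5% |
| 0.5% | 0.5 | 39% |
| 1.0% | 1.0 | 63% |
| 1.3% | 1.3 | 73% |

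These figures count serious ISRs that occur. The number missed by the string can only be smaller or equal.

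**The case against.** The strongest reply is that the protocol is not the only instruction sites receive. Protocol Section 8.5.4 places SAE recording procedures in the SPM, and a fixed upper-case string is what an entry convention kept there might look like. This stands as a possibility. It cannot be confirmed, and the SAP neither cites such a convention nor provides for the case where a site does not follow it.

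Three safeguards also count. Protocol Section 8.4.1 sends every ISR to the ISR form, so a serious one recorded there might enter by the first source. SAP Section 12.10 allows events to be added after data review before the freeze, and Section 8.3 allows the list of events of special interest to change. Protocol Section 8.7.9 requires serious ISRs to be discussed with the Medical Monitor, so the sponsor should know of each. The first depends on resolving the conflict over the form. The second is permissive and sets no ISR criteria. The third makes review feasible but does not place the event in the analysis set.

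A reader might go further and infer that the worst reactions will be missing from every ISR table and figure, or that the severity displays are systematically tilted towards mild. The documents do not support this. Protocol Section 12.4.4 separates serious from severe, and non-serious Grade 3 and 4 ISRs still enter through the form. The two overlap in part: under Protocol Appendix 3, injection site pain is Grade 4 when hospitalization is indicated, and inpatient hospitalization makes an event an SAE. But a top-grade row would read zero wrongly only if the missed event were the only one of that grade. Nor can it be said how often the match would fail. The common-ISR displays, and those of the other drug, would not show a single abscess under any definition.

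**Conclusion.** The point holds as a gap in the SAP's definition and as a conflict between the documents. As written, the SAP admits a serious study-drug ISR only by a literal string that neither supplied document tells sites to use, while the protocol directs every ISR to a form that the SAP calls non-serious. A serious ISR recorded by diagnosis could drop out of the overall ISR outputs and of one drug's set.

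The size is small: one missed case is about 1% of an arm of at most about 100. This rests on two assumptions: that the ISR form really excludes serious events, and that no term convention in the SPM closes the gap. The event would not be lost from the report, the ISR displays are descriptive, and the primary endpoint is untouched. This is a cheap improvement rather than a threat to the study's conclusions.

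**What to change.** Amend SAP Appendix 10, item 12, in three respects.

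1. State which eCRF form holds serious ISRs, and reconcile this with Protocol Section 8.4.1. If a term convention exists in the SPM, cite it.
2. Define serious study-drug ISRs as (a) SAEs coded to preferred terms beginning Injection site and not attributed to a non-study injection, plus (b) SAEs of infection, abscess, haematoma, necrosis or fluid collection at the gluteal injection area, identified by study-physician review of all injection-arm SAEs before each database freeze.
3. Keep the text string as an additional trigger, not as the sole criterion.

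The cost is one SAP paragraph and a short review of a few SAEs per freeze. Much of the information should already exist, because serious ISRs go to the Medical Monitor. The small downside is a judgement on attribution for a handful of events, which should be documented before the freeze.
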